1.1.2 Secondary Objectives

Secondary objectives of this study are to determine if treatment with ezogabine is associated with a reduction in clinical symptoms of depression and anhedonia and with a modulation of behavioral responses to reward.

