3.2 Secondary Endpoints

Secondary endpoints are measured at 5 weeks post-randomization unless otherwise noted. The following secondary endpoints will be analyzed. All secondary analyses will be considered exploratory and will not influence the study “go-no/go” decision.

3.2.1 fMRI Activation within the Reward Circuit

In the same manner as the primary endpoint, fMRI activation in other regions of the reward cortico-striatal circuit (medial prefrontal cortex [mPFC], bilateral dorsal striatum [DS], and anterior cingulate cortex [ACC]), as well as whole-brain analyses, will be measured during the gain cue of the IFT and contrasted with neutral cue.

Similarly, activation during the loss cues of the IFT task will be compared with the fMRI activation in neutral tasks.

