3.2.5 Reward learning

The Probabilistic Reward Task (PRT) will be used as a behavioral assessment to calculate an index of reward learning at baseline (V0) and at the time of the primary outcome assessment (V5).

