5. STATISTICAL METHODOLOGY

5.1 Statistical Methods

All data will be presented by treatment group as well as for the whole sample.

For all baseline, demographic and efficacy variables, data will be summarized and analyzed by randomized treatment group as per ITT.

In summary tables of normally distributed continuous variables, the following descriptive statistics will be used: minimum and maximum, mean, and standard deviation (SD). In summary tables of non-normally distributed variables data will be presented using the minimum, maximum, median and lower and upper quartiles.

In summary tables of categorical variables, counts and percentages will be used. The denominator for each percentage will be the number of patients within the randomization group unless otherwise specified.

Rates of events will be calculated as the ratio of the total number of events recorded divided by the total patient-time in study (months or days). Total patient-time will be

calculated by summing the time (in days) that patients were at risk for a specific event from the time they were randomized in the study until study exit. Rates and 95% confidence intervals will be reported.

For any variable measured at multiple points in time, change from baseline will be calculated as the difference between the value of the variable at a specific point in time (e.g. 5 weeks) minus the baseline value.

Relative change from baseline will be calculated as the value of a parameter at a specific point in time minus the baseline value of the parameter divided by the baseline value of the parameter.

Percent change will be calculated as the relative change multiplied by 100.

Hypothesis testing will be conducted at the 0.05 two-sided significance level for the primary endpoint. No formal hypothesis tests will be conducted for the secondary endpoints, rather, we will calculate estimates and 95% confidence intervals by group.

P-values will be rounded to three decimal places. P-values less than 0.001 will be reported as <0.001 in tables. P-values greater than 0.999 will be reported as >0.999.

Should any of the statistical methods proposed prove unsuitable during data analysis, more appropriate methods will be used. These include data transformation (for example to a logarithmic scale) to satisfy model assumptions such as normally distributed residuals with constant variance, or the application of non-parametric techniques.

Additional ad-hoc analyses may be conducted as deemed appropriate.

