5.4.2 Secondary Endpoints

All secondary analyses will be performed using the ITT population.

As the secondary fMRI outcomes are exploratory analyses, we will present the mean and 95% confidence interval of the difference in change in activation between treatment groups rather than conducting formal hypothesis testing. As with the bilateral VS, a single beta weight for the bilateral DS will be calculated by averaging the beta weights for the left DS and right DS.

Linear mixed effects models will be used to analyze the anhedonia, depression, and general functioning scales that are collected at multiple time points. Slopes will be estimated with 95% confidence intervals by treatment group. Mean change and 95% confidence intervals by group will be presented for measures collected at baseline and primary outcome only.

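### The clinical scales and the PRT are to be reported only arm by arm; the SAP does not commit to the ezogabine-minus-placebo estimate that its secondary objective asks for

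*SAP*

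**What the plan says.** SAP 1.1.2 gives the secondary objective as "to determine if treatment with ezogabine is associated with a reduction in clinical symptoms of depression and anhedonia", together with a modulation of behavioral responses to reward. Protocol 3.2 describes the same aim as examining the effects of ezogabine, in an exploratory manner. SAP 1.2 describes a 1:1 randomized, double-blind, placebo-controlled trial.

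The reporting rules are:

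- **All secondary endpoints (SAP 5.1):** "No formal hypothesis tests will be conducted for the secondary endpoints, rather, we will calculate estimates and 95% confidence intervals by group".
- **Scales at multiple time points (SAP 5.4.2):** linear mixed models, and then "Slopes will be estimated with 95% confidence intervals by treatment group". By the timing in SAP 3.2.2 to 3.2.4 this covers SHAPS, TEPS, ACIPS, SLIPS, QIDS-SR, MADRS and the CGI scales.
- **Measures at V0 and V5 only (SAP 5.4.2):** "Mean change and 95% confidence intervals by group will be presented for measures collected at baseline and primary outcome only". By timing this covers MASQ, WHODAS and the PRT; SAP 5.4.2 does not name the PRT.
- **Secondary fMRI regions (SAP 5.4.2):** "we will present the mean and 95% confidence interval of the difference in change in activation between treatment groups".

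Protocol 16.4 plans only descriptive statistics for the PRT and the clinical and self-report measures. Protocol section 16 gives the SAP precedence where the two differ.

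**The concern.** In a placebo-controlled trial, the effect of a drug on symptoms is the contrast between arms. A slope or mean change within the ezogabine arm also contains placebo response, time and regression to the mean. The sponsor allows for a placebo effect in its own planning: Protocol 16.6 assumes d = 0.15 on the brain measure.

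If the SAP is followed as written, the trial would report two within-arm results per scale and leave the reader to infer the treatment effect. The usual shortcut, checking whether the two intervals overlap or whether one excludes zero and the other does not, is unreliable in both directions. If the investigators later computed the difference, the SAP's purpose statement would oblige them to label it unplanned, although it is the most natural clinical comparison in the trial.

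**Working it through.** **1. Is the contrast committed to anywhere?**

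| Outcome family | Status (SAP 3.2) | Planned estimate | Between-arm difference? |
|---|---|---|---|
| mPFC, DS, ACC activation | exploratory | difference in change, 95% CI | yes |
| Weekly clinical scales | exploratory | slope per arm, 95% CI | no |
| MASQ, WHODAS, PRT | exploratory | mean change per arm, 95% CI | no |

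SAP 3.2 applies one status to all three rows: "All secondary analyses will be considered exploratory and will not influence the study" go/no-go decision. For the fMRI regions, SAP 5.4.2 offers the CI of the difference as the alternative to a formal test. The same reasoning fits the other two rows.

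**2. The plan's own figure.** The only stated precision figure is 85% power for the primary endpoint (SAP 5.4.1): 48 patients, 0.8 SD, correlation 0.6, two-sided 0.05.

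- SD of change = √(2 × (1 − 0.6)) = 0.894.
- SE of the difference = 0.894 × √(2/24) = 0.258.
- Noncentrality = 0.8/0.258 = 3.10 on 46 df, which gives power of 85.8%.

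The figure reproduces. The present point does not depend on it.

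**3. Arm CIs against the CI of the difference.** Assumptions: mean change as the outcome, 24 per arm, complete data, and the SD of change set to 1 in both arms.

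- Half-width for one arm = t(0.975, 23)/√24 = 2.0687/4.899 = 0.422.
- The arm CIs stop overlapping when the observed difference exceeds 2 × 0.4223 = 0.84 (two-sided p about 0.005).
- Half-width for the difference = t(0.975, 46) × √(2/24) = 2.0129 × 0.2887 = 0.581.
- Ratio = 0.8445/0.5811 = 1.45.

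An observed difference between 0.58 and 0.84 SD would therefore show overlapping arm CIs while the CI of the difference excludes zero.

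These half-widths are for mean change. For mixed-model slopes the documents give no variance components. If the two arm slopes are roughly independent with equal standard errors, the large-sample ratio is 2/√2 = 1.41, so the same problem arises.

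**4. How often the two readings part.** The documents give no effect size for any clinical scale, so a range is assumed. From 400,000 simulated trials, with the last column confirmed by the noncentral t:

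| True difference (SD of change) | Arm CIs separate | CI of difference excludes 0 |
|---|---|---|
| 0 | 0.5% | 5.0% |
| 0.5 | 13% | 40% |
| 0.8 | 45% | 77% |
| 0.8/0.894 = 0.894 (fMRI planning values) | 58% | 86% |

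**5. The error in the other direction.** Take assumed mean changes of 0.60 SD on ezogabine and 0.30 SD on placebo.

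- Ezogabine: 0.60 ± 0.42 = 0.18 to 1.02, which excludes zero.
- Placebo: 0.30 ± 0.42 = −0.12 to 0.72, which includes zero.
- Difference: 0.30 ± 0.58 = −0.28 to 0.88, which includes zero.

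Side by side, the arm results could suggest a drug effect that the contrast does not support.

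**The case against.** The best defence has five parts.

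- **Wording.** The phrase *by group* need not exclude a difference. SAP 5.1 applies it to all secondary endpoints, including the fMRI regions that then get one, and the objective does not literally say *versus placebo*. This is fair as far as it goes: the SAP does not forbid the contrast. It still does not commit to it, and a comparative reading of the objective is the natural one in this design.
- **Deliberate split.** Protocol 16.4 already separates the imaging regions, analysed like the primary endpoint, from the scales and the PRT, which are described only. Protocol section 2 leaves the relationship between treatment, circuit activity and clinical outcomes to the R33 phase. So the split may be intended. Neither document gives a reason for withholding the difference, and the SAP has already gone beyond description by adding models and CIs.
- **No overlap rule.** Nothing in the plan says the arms will be compared by CI overlap. That is correct. The percentages above show how such a reading would mislead; they are not operating characteristics of the plan.
- **The difference can be recovered.** For mean change, combining the two half-widths gives √(0.4223² + 0.4223²) = 0.597 SD, against 0.581 SD directly, which is 2.8% wider. This stands for an unadjusted difference in mean change. It leaves the main secondary estimate to the reader's own calculation.
- **It can be done anyway.** The mixed model can produce the contrast, and SAP 5.1 permits ad hoc analyses. Neither is a prespecified commitment.

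**Conclusion.** The concern holds. As written, the SAP commits to within-arm slopes and mean changes for the clinical scales, MASQ, WHODAS and the PRT, and to no ezogabine-minus-placebo estimate, while giving equally exploratory imaging outcomes exactly that. The planned outputs therefore do not contain the estimate that the secondary objective asks about.

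The 0.42, 0.58 and 0.84 SD figures rest on 24 complete patients per arm and equal SDs of change; the simulated percentages also rest on assumed true differences. They illustrate the problem and do not predict any scale's result.

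The consequence is limited to secondary reporting. The primary analysis, the sample size and the go/no-go decision are untouched. The change should be made, but it is not critical to the trial's main conclusion.

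**What to change.** Before unblinding:

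- **SAP 5.1:** extend the secondary-endpoint rule so that estimates and 95% CIs are given by group and for the between-group difference.
- **SAP 5.4.2, weekly scales:** add the ezogabine-minus-placebo difference with its 95% CI from the planned mixed model. Name one contrast, either the difference in slope or the difference in change at V5.
- **SAP 5.4.2, MASQ, WHODAS and PRT:** name these measures and add the between-group difference in change from V0 to V5 with its 95% CI. Baseline adjustment is preferable but not essential to this point.
- **C-SSRS:** SAP 3.2.3 also lists it as a weekly measure. State separately how it will be summarised, since a slope contrast may not suit it.

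Keep the by-group results as description. No p-values are needed, so the exploratory status is unchanged. The cost is one clause in SAP 5.1, two in SAP 5.4.2 plus a line on the C-SSRS, and one added column in the output tables, with no new data.

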5.5 Safety Analysis

All adverse events in this study will be analyzed from the time of randomization. All adverse events will be analyzed using the ITT population.

AEs will be mapped to the MedDRA coding system. The incidence of non-serious AEs and serious AEs will be summarized by System Organ Class, MedDRA Preferred Term and treatment.

The number and percentage of patients with an AE or serious AE will be presented. For the incidence count, a patient will be counted only once for a specific MedDRA Preferred Term, although a MedDRA Preferred Term might be recorded more than once for a particular patient.

The number and rate of each AE will also be presented. Differences in the incidence of individual AEs will be assessed using negative binomial regression with the treatment group as the predictor.

5.6 Interim Analysis

There is no planned interim analysis for this study.

